2.4 Secondary endpoints

2.4.1 Confirmatory secondary endpoints

If the effect of treatment with faster aspart can be confirmed in the primary analysis, the trial also aims to confirm effect of treatment with faster aspart for a number of secondary confirmatory endpoints using a hierarchical (fixed sequence) testing procedure as described in section 2 (General consideration). This is based on a priority ordering of the null-hypotheses, and testing them in this order using the two-sided 95% confidence interval approach until an insignificant result appears. The effect is that rejection of the null hypothesis will only be confirmed for endpoints where all previous null-hypotheses have been rejected in favour of faster aspart.

The confirmatory secondary endpoints are:

- Change from baseline in 1-hour PPG increment 16 weeks after randomisation (meal test)
- Change from baseline in 1,5-anhydroglucitol 16 weeks after randomisation

The steps in the hierarchical testing procedure are as follows:

- Step 1 (Primary analysis): HbA_{1c} non-inferiority of faster aspart versus NovoRapid[®]
- Step 2: 1-hour PPG increment (meal test) superiority of faster aspart versus NovoRapid®
- **Step 3:** HbA_{1c} superiority of faster aspart versus NovoRapid[®]
- Step 4: 1,5-anhydroglucitol superiority of faster aspart versus NovoRapid®

The primary estimand for the primary endpoint will be repeated for the confirmatory secondary endpoints, change from baseline in 1-hour PPG increment (meal test) and change from baseline in 1,5-anhydroglucitol 16 weeks after randomisation. The analyses related to these estimands are defined below and will be used for the decisions to continue or not, throughout the hierarchical testing procedure. These analyses will be based on the FAS and use the in-trial observation period.

Statistical Analysis Plan		Date:	12 February 2019	Novo Nordisk
Trial ID: NN1218-4113	CONFIDENTIAL	Version:	2.0	
UTN: U1111-1180-0636	CONFIDENTIAL	Status:	Final	
EudraCT No.: 2016-000878-38		Page:	16 of 29	

As sensitivity analysis the secondary analysis 4) will also be repeated for the confirmatory secondary endpoints. The analyses will be based on the FAS and using the on-treatment observation period.

Change from baseline in 1-hour PPG increment 16 weeks after randomisation (meal test) (step 2)

As the second step of the hierarchical testing procedure change from baseline in 1-hour PPG increment (meal test) 16 weeks after randomisation will be tested for superiority of faster aspart compared to Novo Rapid[®].

The 1-hour PPG increment will be analysed based on the laboratory measured values in the meal test, and is derived as the 1-hour PPG measurement minus the pre-prandial PG measurement.

The 1-hour PPG increment endpoint will be analysed using the FAS and the in-trial observation period based on a multiple imputation technique where the change from baseline in 1-hour PPG increment at week 16 for subjects with missing value are imputed based on data from subjects in the NovoRapid® arm with non-missing values at week 16. Multiple copies (100 copies) of the full dataset will be generated by imputing missing values based on estimated parameters as follows:

- An analysis of variance model with region and metformin use at baseline (Yes/No) as factors and baseline 1-hour PPG increment as covariate is fitted to the change from baseline in 1-hour PPG increment at week 16 for the NovoRapid® group only. The estimated parameters, and their variances, from this model are used to impute missing values using stochastic simulation at week 16 for subjects in both treatment groups in order to generate 100 complete datasets.
- For each of the complete data sets, the change from baseline to week 16 is analysed using an analysis of variance model with treatment, region and metformin use at baseline (Yes/No) as factors, and baseline 1-hour PPG increment as covariate.
- The estimates and standard deviations for the 100 data sets are pooled to one estimate and associated standard deviation using Rubin's formula. From this, the pooled estimate and 95% confidence interval for the treatment difference are calculated.

The superiority will be assessed by comparing the upper limit of the 95% CI to 0. If the upper 95% CI is below 0 then superiority will be confirmed.

Change from baseline in HbA_{1c} 16 weeks after randomisation (step 3)

Step 3 in the hierarchical testing procedure is to confirm superiority of change from baseline HbA_{1c} 16 weeks after randomisation of the effect of treatment with faster aspart compared to NovoRapid[®]. Superiority will be addressed based on the same 95% CI that was used for addressing the primary

Statistical Analysis Plan		Date:	12 February 2019	Novo Nordisk
Trial ID: NN1218-4113	CONFIDENTIAL	Version:	2.0	
UTN: U1111-1180-0636	CONFIDENTIAL	Status:	Final	
EudraCT No.: 2016-000878-38		Page:	17 of 29	

analysis. Superiority will be confirmed if the upper boundary of the two-sided 95% confidence interval of the mean treatment difference (faster aspart minus NovoRapid®) is below 0.

Change from baseline in 1,5-anhydroglucitol 16 weeks after randomisation (step 4)

Step 4 in the hierarchical testing procedure is to confirm superiority of change from baseline in 1,5-anhydroglucitol 16 weeks after randomisation of the effect of treatment with faster aspart compared to NovoRapid[®]. The endpoint will be analysed based on all planned post baseline measurements until or at 16 weeks after randomisation using a model similar to the primary analysis 1), but with baseline 1,5-anhydroglucitol as covariate. Superiority will be confirmed if the upper boundary of the two-sided 95% confidence interval of the mean treatment difference (faster aspart minus NovoRapid[®]) is below 0.

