At the baseline meal test, the bolus insulin dose should be calculated by the investigator by dividing the digestible carbohydrate content of the standardised meal by a calculated insulin:carbohydrate ratio. The insulin:carbohydrate ratio in this trial is calculated by dividing 500 by the total daily dose (taken from the day before) of both basal and bolus insulin. The calculated dose should be rounded to the nearest whole unit.

Same bolus insulin dose will be used for the meal test at end of treatment. The insulin should be administered subcutaneously in the abdomen in accordance with Table 8–1.

Initiation of meal test

The subject's body weight must be measured before start and a blood sample must be drawn two minutes before intake of the standardised meal.

For the meal test at Visit 14 the subject must receive the bolus insulin that was also used in the runin period.

For the meal test at Visit 30 the subject should receive the bolus trial insulin they were randomised to and have used throughout the treatment period. If subject has been prematurely discontinued they should perform a meal test both at Visit 30A and again at Visit 30; the meal test at Visit 30 should be performed with the marketed bolus product the subject was switched to.

The start of consumption of the liquid meal is defined as time point 0. The subject must consume the liquid meal as quickly as possible and within 12 minutes. The investigator should confirm that the subject consumed the required volume of the standardised liquid meal in the eCRF.

Protocol Trial ID: NN1218-4113 UTN: U1111-1180-0636 EudraCT no.: 2016-000878-38

CONFIDENTIAL

 Date:
 23 February 2018

 Version:
 4.0

 Status:
 Final

 Page:
 43 of 112

Table 8–1 Meal test schedule

Time point (minutes)	Blood sample	SMPG values	Standardised meal	Bolus insulin injection
Before start of meal test		X (within target range 4.0-8.8 mmol/L [71-160 mg/dL])		
-2	X			
0			X	X Insulin injection at the start of the meal
30	X			
60	X	X (as appropriate to ensure		
120	X	subject's safety)		
180	X	1		
240	X	1		
End of meal test		X (for subject's safety)		

Conduct of meal test

The subject should stay in the clinic to have the blood samples drawn after 30 minutes, 1, 2, 3 and 4 hours from the start of the standardised meal, as detailed in Table 8–1. The samples will be analysed by the central laboratory.

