8.5.1 Laboratory assessments for efficacy

Glucose metabolism

Plasma glucose will be measured during the meal test. See section 8.3.1.

FPG is measured in order to evaluate metabolic control. The subject must attend these visits fasting. For definition of fasting, see Section 8.1.5.

A FPG result \leq 3.9 mmol/L (70 mg/dL) should not be reported as a hypoglycaemic episode but as a clinical laboratory AE (CLAE) at the discretion of the investigator (see Section 12.1.1).

The level of 1,5-anhydroglucitol (GlycoMark) is measured in order to evaluate post prandial glucose excursions.

Blood samples will be drawn to determine the HbA_{1c} level in order to evaluate metabolic control.

Fasting C-peptide is measured at randomisation in order to reflect endogenous insulin secretion.

Lipids

Blood samples for lipids will be analysed to determine:

- Total cholesterol
- High density lipoprotein (HDL) cholesterol
- Low density lipoprotein (LDL) cholesterol

Page:

55 of 112

EudraCT no.: 2016-000878-38

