2.1 Sample size calculation

The sample size is determined to ensure a sufficient power for step 1 and step 2 in the hierarchical testing procedure for the primary estimand presented in section $\underline{2}$. The power for step 3 and 4 in the hierarchical testing procedure will also be presented. The sample size is determined using a non-inferiority limit of 0.4% in step 1, which was chosen as described in section 5.2.1 in the protocol. The statistical evaluation will be done as described in sections $\underline{2.3}$ and $\underline{2.4}$.

In previous confirmatory trials where faster aspart has been investigated, the completion rates have been high. Therefore it will be expected that treatment discontinuation might be as low as 10% where trial discontinuation constitutes half of these and with similar withdrawal reasons in the treatment arms.

Power for the non-inferiority step (Step 1) is based on a t-statistic under the assumption of a one-sided test of size 2.5% for the FAS. A mean treatment difference of -0.1% for the comparison between faster aspart and NovoRapid[®] in favour of faster aspart is expected. As trials in this population where data from treatment withdrawn subjects is retrieved is limited, a conservative estimate of the standard deviation (SD) in change from baseline in HbA_{1c} of 0.8% was chosen. The power for superiority in step 3 will be calculated using the same assumptions as for step 1 but without the non-inferiority margin.

For determination of power in step 2 in the hierarchical testing, where change from baseline in 1-hour PPG increment 16 weeks after randomisation is compared between faster aspart and NovoRapid® a t-statistic with a two-sided test of size 5% is used, where the treatment difference is

Statistical Analysis Plan		Date:	12 February 2019	Novo Nordisk
Trial ID: NN1218-4113	CONFIDENTIAL	Version:	2.0	
UTN: U1111-1180-0636	CONFIDENTIAL	Status:	Final	
EudraCT No.: 2016-000878-38		Page:	9 of 29	

expected to be at least 0.6 mmol/L [11 mg/dL]. The SD=3.5 mmol/L [63 mg/dL] in change from baseline in 1-hour PPG increments 16 weeks after randomisation based on laboratory analysed PG in a standardised meal test will be considered reasonable based on trials NN1218-3852 and NN1218-3853.

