The power in step 4, where superiority of faster aspart over NovoRapid $^{\$}$ in change from baseline in 1,5-anhydroglucitol 16 weeks after randomisation is tested a t-statistic with a two-sided test of size 5% is used. The mean treatment difference is expected to be at least 0.2 μ g/mL and an SD of 3.5 μ g/mL will be used based on trials NN1218-3852 and NN1218-3853.

The power calculations are done using proc power in SAS 9.4. Please refer to Table 2–1 for assumptions for the sample size calculation.

Table 2–1 Specifications assumed for sample size calculation

Statistical test	Significance level	Analysis population	Non-inferiority margin	SD	Mean difference	Randomisation scheme
Step 1 2-group t-tes	t One-sided 2.5 %	FAS	0.4 % (absolute)	0.8 %	-0.1 %	1:1
Step 2 2-group t-tes	t Two-sided 5.0%	FAS	NA	3.5 mmol/L	0.6 mmol/L	1:1
Step 3 2-group t-tes	t Two-sided 5.0%	FAS	NA	0.8 %	-0.1 %	1:1
Step 4 2-group t-tes	t Two-sided 5.0%	FAS	NA	$3.5~\mu g/mL$	$0.2~\mu\text{g/mL}$	1:1

In Table 2–2 the sensitivity of the sample size to the power shown for three different sizes of FAS. Three different choices of the mean difference are used to calculate the power in step 2.

Table 2–2 Sensitivity of sample size to power

N total	N per arm	Step 1			Step 2			Step 3			Step 4		
FAS	FAS	Mean diff (%)	SD (%)	Power (%)	Mean diff (mmol/L)	SD (mmol/L)	Power (%)	Mean diff (%)		Power (%)	Mean diff (μg/mL)	SD (μg/mL)	Power (%)
		-0.1	0.8	>99.9	0.5	3.5	58.1	-0.1	0.8	47.4	0.2	3.5	13.9
920	460	-0.1	0.8	>99.9	0.6	3.5	73.8	-0.1	0.8	47.4	0.2	3.5	13.9
		-0.1	0.8	>99.9	0.7	3.5	85.8	-0.1	0.8	47.4	0.2	3.5	13.9
		-0.1	0.8	>99.9	0.5	3.5	64.7	-0.1	0.8	53.4	0.2	3.5	15.5
1072	536	-0.1	0.8	>99.9	0.6	3.5	80.1	-0.1	0.8	53.4	0.2	3.5	15.5
		-0.1	0.8	>99.9	0.7	3.5	90.5	-0.1	0.8	53.4	0.2	3.5	15.5
		-0.1	0.8	>99.9	0.5	3.5	70.4	-0.1	0.8	58.9	0.2	3.5	17.0
1224	612	-0.1	0.8	>99.9	0.6	3.5	85.0	-0.1	0.8	58.9	0.2	3.5	17.0
		-0.1	0.8	>99.9	0.7	3.5	93.8	-0.1	0.8	58.9	0.2	3.5	17.0

In conclusion, 1072 subjects in the FAS (536 subjects per group) will ensure a marginal power of >99.9% to show non-inferiority in step 1, given that the actual treatment difference is -0.1%, and a marginal power of 80.1% to show superiority in step 2, given that the actual treatment difference is 0.6 mmol/L.

Assuming a screening failure rate of 30% and run-in failure rate of 15%, 1803 subjects should be screened for inclusion in the trial.

2.2 **Definition of analysis sets**

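### Step 2 could be given slightly more precision at almost no cost: its only continuous covariate is the baseline 1-hour increment, while separate baseline glucose values and fasting C-peptide are already collected

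*SAP*

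**What the plan says.** SAP 2.4.1 tests the change from baseline in 1-hour PPG increment as step 2 of the fixed sequence. Steps 3 (HbA1c superiority) and 4 (1,5-anhydroglucitol) can be claimed only if step 2 succeeds. The analysis model has treatment, region and metformin use as factors and "baseline 1-hour PPG increment as covariate". The imputation model has the same terms without treatment and is fitted in the NovoRapid arm only. Protocol version 4.0, section 17.4.1, specifies the same terms.

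The increment "is derived as the 1-hour PPG measurement minus the pre-prandial PG measurement". The baseline meal test takes place at Visit 14 before randomisation and its samples go to the central laboratory (Protocol 8.3.1), so both components of the baseline increment are available as separate values.

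Protocol 8.5.1 states: "Fasting C-peptide is measured at randomisation in order to reflect endogenous insulin secretion". The SAP uses this measurement in no model.

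**The concern.** Entering only the difference between two baseline values forces their coefficients to be equal in size and opposite in sign. If the pre-prandial and 1-hour values predict the week 16 change with different strength, the model cannot use that. C-peptide is collected because it reflects the subject's own insulin secretion, which could bear on the response to a meal, and it is left out.

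Prognostic baseline covariates in a linear model of a randomised comparison leave the target mean difference unchanged and can reduce its standard error. Any precision gained here would count: the sample size was set on steps 1 and 2, step 1 has more than 99.9% power, and step 2 is the step at 80.1% that opens the rest of the sequence.

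**Working it through.** **Inputs from SAP 2.1.** Step 2 test: "a t-statistic with a two-sided test of size 5% is used". Difference 0.6 mmol/L, 536 subjects per arm. Standard deviation: "The SD=3.5 mmol/L [63 mg/dL] in change from" baseline, so 3.5 mmol/L is the SD of the raw change and not a residual SD.

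**Plan's own figure.** Standard error = 3.5 × √(2/536) = 0.2138. Noncentrality = 0.6/0.2138 = 2.806. The two-sided 5% noncentral t with 1070 degrees of freedom gives 80.06%, and the usual normal approximation gives 80.13%. The stated 80.1% reproduces. It belongs to an unadjusted two-group comparison.

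**Credit the planned baseline covariate.** Let rho be the correlation between baseline and week 16 increment, with equal variances. Adjusting for baseline gives residual SD = 3.5 × √((1 + rho)/2). The documents give no rho, so 0.3, 0.5 and 0.7 are assumed. Region and metformin use are given no credit.

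**Add the proposed covariates.** Let r be their partial R-squared beyond the planned covariates, also assumed. The residual SD is then multiplied by √(1 − r).

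| Assumed rho | Residual SD, planned model | Power, planned model | r = 1% | r = 5% | r = 10% |
|---|---|---|---|---|---|
| 0.3 | 2.822 | 93.5% | +0.2 | +1.1 | +2.1 |
| 0.5 | 3.031 | 89.9% | +0.3 | +1.4 | +2.8 |
| 0.7 | 3.227 | 86.0% | +0.3 | +1.7 | +3.3 |

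Gains are in percentage points. For example, at rho = 0.5 and r = 5%, the SD is 3.031 × √0.95 = 2.954 and power is 91.3%, against 89.9%.

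**How much can splitting the increment add by itself?** An illustrative model takes pre-prandial value = usual level + day-to-day error, and 1-hour value = usual level + meal rise + error. The SD of the change was held at 3.5. The total pre-prandial SD was limited to about 1.4 mmol/L, an assumption suggested by the 4.0–8.8 mmol/L pre-meal range in Protocol 8.3.1. Over 24 combinations of assumed variances, the partial R-squared from splitting ran from 0 to about 4.6%, and 22 of the 24 were below 2.5%.

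**Cost in parameters.** The increment and both of its components cannot be fitted together because they are exactly linearly dependent. Replacing the increment with the two values adds one parameter and log C-peptide adds another: two degrees of freedom out of more than 1000. The planned model is the special case with equal and opposite glucose coefficients and a zero coefficient for C-peptide.

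**The case against.** The strongest reply is that this is a preference whose benefit cannot be shown. The planned model is legitimate, identical in the protocol and SAP, and more precise than the calculation that sized the trial if baseline and week 16 values are at all typically correlated. No document gives an R-squared for C-peptide or for the split values. Protocol 8.5.1 says what C-peptide reflects, not that it predicts the change in increment once the baseline increment is known. Two design features point to a small gain: the pre-meal range narrows the spread of the pre-prandial value, and the same bolus dose is used at both tests, so the baseline increment already carries much of what is stable about a subject. All of this stands, and it limits the size of the point.

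Several stronger readings are tempting, and the documents do not support them:

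- A reader might infer that step 2 adjusts for nothing but the increment and ignores the glucose values. Region and metformin use are also in the model, and the two values enter through their difference.
- A reader might apply the extra R-squared directly to SD 3.5 and report a rise from 80.1% to 82.0% (5%) or 84.0% (10%). That starts from an unadjusted SD, although the planned analysis already adjusts for baseline.
- A reader might add that the run-in bolus product should be a covariate, because at Visit 14 the subject "must receive the bolus insulin that was also used in the" run-in period. The documents give no basis for its predictive value, and nothing is proposed for it here.

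The remaining objection is that changing a confirmatory model has consequences. It does: it departs from the protocol text and carries over to other meal-test models. Both are manageable before unblinding.

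**Conclusion.** A minor, optional precision improvement on a gating test. The planned analysis is valid and need not be changed for the trial's conclusions to stand.

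The unused information is a matter of record: one continuous covariate, two laboratory values reduced to their difference, and a C-peptide measurement in no model. The size of the benefit is not. After crediting the planned baseline adjustment, the gain in step 2 power is about 0.2–0.3 point at 1% extra partial R-squared, 1.1–1.7 at 5% and 2.1–3.3 at 10%, and it may be near zero. These figures rest on assumed values of rho and r, equal variances at the two tests, a difference of 0.6 mmol/L and complete data on 536 subjects per arm.

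**What to change.** Before unblinding, amend step 2 in SAP 2.4.1:

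1. Replace the baseline 1-hour increment with two covariates, baseline pre-prandial plasma glucose and baseline 1-hour PPG.
2. Add log fasting C-peptide at Visit 14.
3. Use the same terms in the NovoRapid-arm imputation model and in the analysis model.
4. Fill a missing log C-peptide with the overall mean of log C-peptide, both arms pooled.
5. Carry the terms over to the meal-test models that SAP 2.4.2.1 defines by reference to step 2, using the baseline PPG of the matching time point, and to the meal-test supplementary analyses in SAP 2.5.
6. Record the change and its reason in SAP section 3.

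The cost is SAP wording, the matching programming and two degrees of freedom. No new data are needed. The choice must be fixed without sight of treatment allocation, because a covariate set chosen afterwards would weaken a confirmatory test for a small gain.

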Step 3 in the hierarchical testing procedure is to confirm superiority of change from baseline HbA_{1c} 16 weeks after randomisation of the effect of treatment with faster aspart compared to NovoRapid[®]. Superiority will be based on the same 95% CI that was used for addressing the primary analysis. Superiority will be confirmed if the upper boundary of the two-sided 95% confidence interval of the mean treatment difference (faster aspart minus NovoRapid[®]) is below 0%.

Change from baseline in 1,5-anhydroglucitol 16 weeks after randomisation (step 4)

Step 4 in the hierarchical testing procedure is to confirm superiority of change from baseline 1,5-anhydroglucitol 16 weeks after randomisation of the effect of treatment with faster aspart compared to NovoRapid[®]. The endpoint will be analysed based on all planned post baseline measurements until or at 16 weeks after randomisation using a model similar to the primary analysis 1), but with baseline 1,5-anhydroglucitol as covariate. Superiority will be confirmed if the upper boundary of the two-sided 95% confidence interval of the mean treatment difference (faster aspart minus NovoRapid[®]) is below 0.

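### Step 4 confirms superiority on 1,5-anhydroglucitol when faster aspart gives the lower, worse value; the rule tests the wrong end of the confidence interval

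*SAP*

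**What the plan says.** The fixed sequence runs: HbA1c non-inferiority, superiority on 1-hour PPG increment, HbA1c superiority, then 1,5-AG superiority. Section 2 of the SAP and section 17 of the Protocol require each null hypothesis to be rejected in the direction that favours faster aspart before the next is considered.

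For step 4, SAP section 2.4.1 uses the primary analysis model, "but with baseline 1,5-anhydroglucitol as covariate. Superiority will be confirmed if the upper boundary of the two-sided 95% confidence interval of the mean treatment". The end of that sentence in the SAP sets the contrast and the threshold: "difference (faster aspart minus NovoRapid®) is below 0". Protocol v4.0 section 17.4.1 gives the same instruction ("model similar to the primary analysis 1), but with baseline 1,5-anhydroglucitol as covariate. Superiority will be confirmed if the upper boundary"), and so does v2.0. SAP section 3, which lists the changes and clarifications made to the protocol's analyses, does not mention it.

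Protocol section 8.5.1 says that 1,5-AG "is measured in order to evaluate post prandial glucose excursions". Neither document says whether a higher or a lower value is favourable.

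In the sample size section (SAP 2.1), the step 4 entry reads "The mean treatment difference is expected to be at least 0.2" µg/mL, with an SD of 3.5 µg/mL. The HbA1c benefit carries a sign: "A mean treatment difference of -0.1% for the comparison between faster aspart and" NovoRapid. The step 2 benefit, 0.6 mmol/L, does not.

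**The concern.** The step 4 rule has the same form as the rules for HbA1c and PPG increment, where a negative difference is a benefit. 1,5-AG behaves in the opposite way. It is lost in the urine when glucose is high, so its level falls as excursions increase and rises as they lessen. If faster aspart does what the secondary objective claims, faster aspart minus NovoRapid will be positive. The rule asks for it to be negative.

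Step 4 is an alpha-controlled claim about postprandial glucose excursions. Followed literally, the rule would almost always deny that claim when it is true, and could grant it when faster aspart is worse.

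**Working it through.** **Inputs, all from SAP section 2.1 and Table 2–2:** 536 per arm; SD 3.5 µg/mL; difference 0.2 µg/mL; and the test basis ("tested a t-statistic with a two-sided test of size 5% is used").

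**Standard error and interval width.** SE = 3.5 × √(2/536) = 0.2138. Degrees of freedom = 2 × 536 − 2 = 1070. The 95% half-width is 0.42 µg/mL.

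**Reproducing the plan's power.** The noncentrality is 0.2/0.2138 = 0.935. With the noncentral t distribution:

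- P(lower limit above 0) = 0.1526
- P(upper limit below 0) = 0.0019
- Sum = 0.1545, against 15.5% in Table 2–2

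The same method gives 13.9% at 460 per arm and 17.0% at 612, also as tabulated. The inputs are therefore the ones the plan used. The tabulated figure adds both tails, so it does not depend on the sign of the difference. The decision rule uses only one tail.

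**Probability of declaring superiority in step 4, by true difference (faster aspart minus NovoRapid), step 4 taken alone:**

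| True difference (µg/mL) | Meaning for faster aspart | Rule as written (upper limit < 0) | Reversed rule (lower limit > 0) |
|---|---|---|---|
| +0.4 | better | 0.006% | 46.4% |
| +0.2 | better (planned size) | 0.19% | 15.3% |
| 0 | no difference | 2.5% | 2.5% |
| −0.2 | worse | 15.3% | 0.19% |
| −0.4 | worse | 46.4% | 0.006% |
| −0.6 | worse | 80.1% | below 0.001% |

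**What this means for a single result.** With a half-width of 0.42, an observed difference of +0.5 gives an interval of about 0.08 to 0.92. That is clear evidence for faster aspart, and the written rule is not met. An observed −0.5 gives about −0.92 to −0.08, which is clear evidence against faster aspart, and the written rule declares superiority.

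**Consistency with the rest of the plan.** The general clause requires rejection in favour of faster aspart, which for this marker means a positive difference. The step 4 rule requires a negative one. No result can satisfy both.

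**The case against.** **The favourable direction is not in the documents.** This is correct: the point rests on what the assay measures. It needs no figure and no cited study, and it is as elementary as lower HbA1c being better, which the plan also leaves implicit. The premise stands, and it should be stated openly as an outside premise.

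**The unsigned 0.2 proves nothing.** This also stands. Step 2 gives its benefit as an unsigned 0.6 with an upper-limit-below-0 rule, so these entries may simply be magnitudes. The contrast with the signed −0.1% for HbA1c fits the conclusion but does not establish it.

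**The stated power and the error rate at zero are right.** Both are. The two-sided 15.5% is correct arithmetic, and at a true difference of zero either rule rejects 2.5% of the time. But 15.5% is not the chance of success under the written rule when the benefit is positive. The 2.5% bound on false claims also fails once faster aspart is truly worse, as the lower rows of the table show.

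**Step 4 is last and hard to reach.** Steps 1 to 3 cannot be affected. Under the planning assumptions the gate opens at most 53.4% of the time, the marginal power of step 3. A true worsening of 1,5-AG in a trial that has already shown superior PPG increment and HbA1c is unlikely, so the false-claim probabilities should not be read as unconditional risks. The likelier failure is the other one: once steps 2 and 3 have succeeded, 1,5-AG would be expected to rise, and the rule then blocks the claim.

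**Readers will see the estimate and interval anyway.** They will, but the confirmatory conclusion is set by the prespecified rule.

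**Conclusion.** The concern holds. The step 4 criterion in both documents is reversed for this marker and contradicts the plan's own requirement that rejections favour faster aspart. At the planned effect size it cuts the chance of confirming a true benefit from 15.3% to 0.19%, and it gives a worsening of the same size the 15.3% chance instead.

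The conclusion rests on 1,5-AG being higher when glucose excursions are fewer. The probabilities also assume 536 per arm, SD 3.5 µg/mL and an unadjusted two-sample t-test, as in the plan's own calculation; baseline adjustment would change their size but not their direction. The primary conclusion and steps 2 and 3 are not touched. It should still be corrected, because a confirmatory rule that is wrong as written leaves the analyst either to follow it or to depart from the plan.

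**What to change.** In step 4 of SAP section 2.4.1 and Protocol section 17.4.1, replace the criterion with: superiority is confirmed if the lower limit of the two-sided 95% confidence interval for faster aspart minus NovoRapid in change from baseline in 1,5-AG is above 0. State in the same place that a higher value is favourable, and list the correction in SAP section 3.

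For clarity, sign the assumed differences in Protocol Table 17–1 and SAP Table 2–1: −0.6 mmol/L for PPG increment and +0.2 µg/mL for 1,5-AG, with the matching sensitivity tables to follow.

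The cost is one sentence in each document plus the table signs. No new data, sample size or alpha is needed, provided the change is made before unblinding. If treatment codes have already been opened, the correction should be dated and declared as made after unblinding, with the pharmacological reason given, because reversing a confirmatory criterion at that stage is otherwise hard to defend.
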